## 25. COACHING TRACKING AND COMPLIANCE WITH SESSION ATTENDANCE

The compliance with health coaching will be assessed by completion of records on session attendance on REDCap. Sessions will be recorded as completed or missed and reasons for missed sessions will be recorded.

### Coaching evaluation

At the completion of each session, health coaches will self-evaluate the session using the Coaching Evaluation questionnaire on REDCap. In addition, a random 10% of recordings will be evaluated by the coach trainer and supervisor to track the quality of coaching and identify any potential areas of improvement. This will be used to guide ongoing supervision of the coaches.

Addition Information to track study procedures on study completion
Feedback from health coaches on implementation of intervention
Number of participants who are (1) eligible, (2) recruited, (3) randomised, (4) withdrawn or lost to follow-up
Number of coaching sessions carried out in intervention group
Completion rate of case record forms; (1) number of forms completed; (2) average completion of individual forms

---

## 26. ONGOING SUPERVISION

On completion of the initial 6 sessions, coaches will be asked to practice coaching with each other, and friends and family. Once coaching with study participants commences, the coaching trainer will provide regular supervision and advice by way of a monthly coaching supervision meeting. Here coaches will share their experiences and receive feedback and advise on handling various scenarios. The meetings will be audio-recorded for training purposes (to be shared with the coaching team only).

---

## 27. REPORTING AND COMPLIANCE OF INTERVENTION DELIVERY

At the end of each coaching session, coaches will complete the coaching compliance questionnaire on REDCap. This will record when the session took place, the length of the session, the coaches self-rating of how well they judged the session to have gone, and any relevant notes as free text. In addition, a random 10% of interviews will be reviewed by the health coach trainer and given a rating for compliance. If a session was missed, the reasons for this and the plans to make up for this missed session will be recorded.

The intervention will combine educational material and intensive HWC coaching. Participants allocated to the HWC group will have 12 individual coaching sessions over 6 months with trained HWC coaches, of which 4 sessions are carried out weekly, 6 sessions fortnightly and the remaining two sessions monthly. The initial two sessions and the final session will be conducted face-to-face and remaining coaching sessions via telephone. Between the final coaching session and the 12-month assessment, HWC participants will receive a short monthly telephone call from their coach to encourage maintenance of behaviour change. Coaching sessions will take up to 1 hour initially, with later sessions lasting about 30 minutes. IG participants will be provided with tools to assist with behaviour changes.

---

## 28. ASSESSMENT OF COACHING AGAINST ICF CORE COMPETENCIES

The coaching sessions will be evaluated by the coaching trainer against the following competencies (as listed in the case record forms):

**Demonstrates Ethical Practice.** Definition: Understands and consistently applies coaching ethics and standards of coaching

**Embodies a Coaching Mindset.** Definition: Develops and maintains a mindset that is open, curious, flexible and client-centered

**Establishes and Maintains Agreements.** Definition: Partners with the client and relevant stakeholders to create clear agreements about the coaching relationship, process, plans and goals. Establishes agreements for the overall coaching engagement as well as those for each coaching session.

**Cultivates Trust and Safety.** Definition: Partners with the client to create a safe, supportive environment that allows the client to share freely. Maintains a relationship of mutual respect and trust.

**Maintains Presence.** Definition: Is fully conscious and present with the client, employing a style that is open, flexible, grounded and confident

### USUAL CARE

Participants in the UC group will be informed of their group assignment post randomisation. UC participants will receive telephone assessments at 3, 9 and 12 months, and a face-to-face assessment at 6 months post randomisation. They will not be informed about the HWC intervention.

### DATA COLLECTION AND FOLLOW-UP

Research assistants (RAs) will be provided training and ongoing supervision to conduct assessments. All assessments will be conducted in a standardised manner in accordance the Protocol. The Project Manager will conduct the randomisation and assign cases to the RAs. RAs will be blinded to the treatment group.

---

## 29. OUTCOME ASSESSMENTS (SEE TABLE 1 FOR THE FULL LIST OF OUTCOMES)

**Baseline:** The baseline assessment will be conducted prior to randomisation, and within 6 weeks of the index event. The Baseline assessment will be conducted in-person. The initial part of the assessment will be used to determine the full eligibility of the participant for the TIIPS trial. The full assessment will be completed for eligible participants only, and will include all measures required to analyse the primary and secondary outcomes

**3 months** (plus or minus 2 weeks from date of randomisation): The assessment will be conducted by telephone only, and will assess secondary outcomes.

**6 months** (primary outcome) (plus or minus 2 weeks from date of randomisation): The 6- month assessment be conducted in-person and will re-assess the primary outcome as well as secondary outcomes.

**9 months** (plus or minus 2 weeks from date of randomisation): The assessment will be conducted by telephone only, and will assess secondary outcomes.

**12 months** (plus or minus 2 weeks from date of randomisation): The assessment will be conducted by telephone only, and will assess secondary outcomes.

---

## 30. PRIMARY END POINTS

The primary end-point will be measured at 6 months post randomisation. The primary end-point will be the difference in the mean change in systolic blood pressure at 6 months post-randomisation between UC and HWC.

---

## 31. SECONDARY END POINTS

Secondary outcomes include: (1) difference in the mean change in the LS7 scale score at 6 months post-randomisation between UC and HWC (2) the change in individual lifestyle components of the LS7 scale (BMI, smoking, physical activity, and diet) at 6 and 12 months; (3) diastolic BP (mmHg); (4) quality of life (EQ-5D-5L), (5) awareness of stroke risk factors and warning signs, (6) medication adherence (7) cognitive outcomes (8) adverse events including hospitalisations; and (9) health service use and costs.

The LS7 scale includes BP, cholesterol, blood glucose, BMI, smoking, physical activity, and diet. The score of LS7 will be calculated by providing 2 points for ideal, 1 point for intermediate, and 0

points for poor status of each of the 7 individual factors. Ideal levels of health factors were: non-smoker or quit >1 year ago; BMI <25 kg/m^2; BP <120/80 mm Hg; total cholesterol <200 mg/dL; fasting blood glucose <100 mg/dL; ≥150 min/week of physical activity; and a healthy diet score (≥4 components). Study participants who were treated to target levels for hypercholesterolemia, hypertension, or diabetes mellitus were classified as intermediate for the respective health factor. Thus, the LS7 summary score will range from 0 to a maximum of 14 points, with a higher score indicating healthier status.

## WITHDRAWAL

Participants will be able to withdraw at any time during the trial without needing to provide a reason. Once a participant has withdrawn, there will be no further follow-up phone calls and data collection. The RA will record the withdrawal and the approximate date of withdrawal, and the reasons for withdrawal if provided. Participants will be informed that any information about them that has already been collected, analysed and/or included in a publication by the study, will not be able to be destroyed. This will be outlined in the Participant Information Sheet and Consent Form. A participant may be withdrawn from the TIIPS trial if:

1. The participant makes a voluntary decision to withdraw from the trial.
2. The trial is terminated.

## PROTOCOL VIOLATIONS

Any significant protocol violation must be documented and reported to the Study Manager and Operations Committee. A protocol violation is defined as a failure to adhere to the pre-specified trial protocol. Examples are ineligible participants who were included in the trial by mistake and those for whom the intervention or other procedure differed from that outlined in the protocol.

The study manager will maintain all protocol violations, and amendments/changes to the study protocol and operational decisions about the study.

## STATISTICAL ANALYSES

---

### 32. POWER CALCULATION

The sample of 360 participants will provide a simulated 90% statistical power (two sided  $\alpha=0.05$ ,  $\beta=0.10$ ) to detect a clinically significant 6 mmHg (SD $\pm$ 20) difference in systolic blood pressure change at 6 months post-randomisation, assuming 20% non-compliance/loss to follow-up.

Based on our RIBURST data (a observational stroke risk study)[94] data in NZ general population (n=1265, with 0.07% incident stroke or TIA), the required sample size (n=360) will also provide 90% power (2-sided alpha) to detect 20% relative risk reduction in 5-year absolute risk of stroke. The estimated 5-year risk of stroke after TIA and minor stroke in NZ appeared to be greater than that in Europe,[4] likely due to greater risk of stroke in Māori and Pacific people constituting 20% of the NZ RIBURST Study population.

---

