### 4. MEASURING CARDIOVASCULAR RISK.

Testing an intervention that targets brain and heart health requires an evidence-based, relevant and reliable measure to determine its efficacy. Hypertension or high blood pressure is the most significant risk factor for stroke. The landmark INTERSTROKE study conducted in over twenty-six thousand participants in 32 countries showed that a history of hypertension increased the risk of stroke by 2.64-fold, and was the most significant risk factor for stroke. [30] Moreover the Global Burden of Diseases studies have shown that high systolic blood pressure is the leading risk factor contributing to the burden of stroke with 79.6 million disability adjusted life years lost (DALYs), which equated to 55% of DALYs. [31, 32]. A meta-analysis of 48 randomised trials evaluating the effects of blood pressure lowering in the risk of major CVD events (including stroke) found that a reduction of 5 mm Hg systolic blood pressure was associated with an 11% reduction in major cardiovascular events in people with previous cardiovascular disease.[33]

A recent study from Finland examined the association of the LS7 with the risk of stroke men without a history of stroke. In terms of absolute blood pressure, the study found that average blood pressures were  $138.2 \pm 16.6$  mm Hg in the poor,  $132.0 \pm 16.5$  mm Hg in the average and  $118.6 \pm 12.4$  mm Hg in the optimum categories of the LS7.[34] Thus, an improvement from poor to ideal blood pressures could reduce systolic blood pressure by up to 13 mm Hg. The Novel Approach to Cardiovascular Health By Optimizing Risk Management (ANCHOR) trial demonstrated a 4.5 mm Hg reduction in systolic blood pressure using a behaviour change intervention in people with an increased risk of CVD. [35] While the incidence of stroke and new vascular events would be ideal primary outcomes, this outcome would require long term follow-up and a prohibitively large sample size [18, 24, 36]. Blood pressure is also considered as a practical paradigm for preventing cardiovascular disease and improving total health. [33]

Given the increased risk of secondary events in this population, a 6 mm Hg difference in systolic blood pressure is plausible with an effective intervention.[37]

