## RANDOMISATION

Randomisation will be conducted in REDCap. On completion of the baseline assessment, the study manager will randomise participants into HWC (n=180) or UC (n=180). Stratified minimisation randomisation will be used to balance prognostic factors: age (<55, ≥55 years, sex (Male, Female), ethnicity (European, Pacific, Māori, Asian and MELAA (Middle Eastern, Latin American and African)).

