### 34. INFERENCE ANALYSES

Intention to treat (ITT)[95] analyses and per protocol analysis will be used. To address the primary hypothesis ANCOVA will be used to compare the difference in systolic blood pressure at 6-months post randomisation between the HWC and usual care groups, accounting for baseline stratification factors: (age, gender and ethnicity), referral centres, geographical region and known influential clinical characteristics (e.g., comorbidities). To address the secondary hypotheses linear mixed effects (LME) repeated measures models will be used to investigate the differences in (1) adherence to medication (2) health-related quality of life (3) incidence of new vascular events including death (4) life satisfaction (5) cognition (6) mood) and (7) health service utilisation costs between the HWC and Usual care groups, and by ethnicity (sub-group analysis) at 6-months (plus

life-style and adherence at 1-year post-randomisation. These LMEs will model effect of time (baseline, 3-, 6- 9- and 12-months (medication adherence, lifestyle and awareness at only 12 months), post-randomisation whilst accounting for key demographic stratification factors known to confound with outcomes. Any data not collected within 6-weeks of the follow-up points will be classified as missing data. Baseline covariates of age, sex, most recent blood pressure measure and any additional variables predictive of outcome data will be included in the imputation model.[46] The reasons for missingness and the reasons will be recorded and accounted for. Sensitivity analyses will be conducted to test the assumptions of the model (including a complete case analysis in which only subjects with complete data are included). Familywise error control will be used to account for the multiplicity of tests. Inferences will be based on a 5% significance level and two-sided alternatives.

For the analysis of - CVD adverse outcomes (fatal and nonfatal stroke, TIA, myocardial infarction and heart failure, death attributable to CVD and all-cause mortality), we will use Kaplan-Meier life-test and estimate the hazard ratios (HR) and adjusted HR using time-to-event Cox regression analysis. Time to event analysis will include recurrent events and time-dependant variables where appropriate.

Competing risk method will also be applied to compare the CVD adverse outcomes between the two interventional groups, accounting for mortality outcome.

---

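### The 90% power claimed for a 20% relative reduction in 5-year stroke risk has no usable basis in the protocol: the only input given is an incidence that cannot produce it

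*Protocol*

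**What the plan says.** After the power statement for systolic blood pressure, section 32 (Power calculation) adds a second claim: the same 360 participants "will also provide 90% power (2-sided alpha) to detect 20% relative risk reduction in 5-year absolute risk of stroke". The stated basis is an observational stroke risk study, described as "data in NZ general population" and summarised as "n=1265, with 0.07% incident stroke or TIA". Section 32 gives no control mean, SD, 5-year stroke rate for patients after TIA or minor stroke, test, or attrition allowance for this claim. It remarks that 5-year stroke risk after TIA and minor stroke seems higher in New Zealand than in Europe, but attaches no figure.

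Elsewhere, 5-year absolute risk is the output of the Stroke Riskometer app. Section 11 lists it as the third secondary outcome, Table 1 ticks it at baseline and 6 months, and the follow-up form records it as a percentage. Section 31, which lists the secondary end points again, omits it. On stroke and new vascular events as a primary outcome, section 4 says that "this outcome would require long term follow-up and a prohibitively large sample size".

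**The concern.** A power statement should follow from its inputs, and this one does not. The wording (relative risk reduction, incident stroke or TIA) is that of an event comparison, and the only input is an incidence. Yet the trial observes no 5-year events, and section 4 has already set event outcomes aside as unaffordable. If a continuous predicted-risk score is meant, an incidence says nothing about its spread, so power cannot be derived from it.

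This is the only secondary outcome with its own power figure. A reader could believe that the trial is powered for stroke risk, or could take a non-significant difference as good evidence of no benefit. The Health Economic Evaluation section also names change in absolute 5-year risk as one possible input, beside LS7, for modelling strokes averted.

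**Working it through.** **Inputs**

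- 360 randomised 1:1, so 180 per arm (Randomisation).
- 20% non-compliance or loss (section 32), treated here entirely as loss: 0.8 × 180 = 144 per arm, 288 in all.
- Two-sided 5%. The claim itself states no alpha; section 34 says "Inferences will be based on a 5% significance level and two-sided alternatives".
- Effect: 20% relative reduction, so p2 = 0.8 × p1, or a mean difference of 0.2 × the control mean.
- Event rates: 0.07% (section 32), and up to 26% within four years after TIA (section 1). The 26% counts all new vascular events, so it is generous as a stand-in for stroke.

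**The stated input**

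0.0007 × 1265 = 0.89 of a person. One case would be 1/1265 = 0.079%. The printed figure may be a truncation of that, but it rests on at most about one case and describes the general population, not this trial's patients.

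**Reading 1: comparison of events**

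Power = Φ[(d − 1.96 × SE0)/SE1], with d = p1 − p2, SE0 = √[2 × p̄(1 − p̄)/n] and SE1 = √{[p1(1 − p1) + p2(1 − p2)]/n}.

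*At 0.07%, n = 180:* p2 = 0.00056, d = 0.00014, SE0 ≈ SE1 ≈ 0.002645. (0.00014 − 0.005184)/0.002645 = −1.907, so power is 2.8% in the intended direction. Adding the opposite tail gives 5.0%.

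*At 26%, n = 180:* p2 = 0.208, d = 0.052, SE0 = 0.04463, SE1 = 0.04454. (0.052 − 0.08747)/0.04454 = −0.796, so power is 21.3%.

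| Control rate | Power, 180 per arm | Power, 144 per arm | Needed per arm for 90% |
|---|---|---|---|
| 0.07% | 2.8% (5.0% both tails) | 2.8% (5.0% both tails) | about 675,000 |
| 26% | 21.3% | 17.9% | 1,391 |

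With 180 per arm, 90% power would need a control risk of about 78%. The stated 90% is not reproduced at any event rate in the document. Follow-up ends at 12 months (section 18), so five-year events could not be counted in any case.

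**Reading 2: comparison of mean Riskometer predicted risk**

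Let CV = SD/mean. Power = Φ[0.2/(CV × √(2/n)) − 1.96]. For 90%, 1.960 + 1.2816 = 3.2415, so the largest CV allowed is 0.2/(3.2415 × √(2/n)):

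- 144 per arm: 0.2/(3.2415 × 0.11785) = 0.524.
- 180 per arm: 0.2/(3.2415 × 0.10541) = 0.585.

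The protocol gives no CV. Over an assumed range, unadjusted:

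| Assumed CV | Power, 144 per arm | Power, 180 per arm |
|---|---|---|
| 0.50 | 92% | 97% |
| 0.75 | 62% | 72% |
| 1.00 | 40% | 47.5% |

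Adjusting for a baseline score with correlation r multiplies the residual SD by √(1 − r²), so the limit rises to 0.524/√(1 − r²). With 144 per arm and r assumed:

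| Assumed r | Largest CV for 90% | Power at CV 0.8 |
|---|---|---|
| 0.6 | 0.524/0.800 = 0.65 | 76% |
| 0.7 | 0.524/0.714 = 0.73 | 84% |
| 0.8 | 0.524/0.600 = 0.87 | 94% |

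On this reading 90% may or may not be met. The answer depends on two quantities, CV and r, that the document does not supply.

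**The case against.** The strongest reply is that the event figures test a comparison the trial does not propose. Section 11, Table 1 and the follow-up form all use 5-year absolute risk for the Riskometer output, the reference cited in the disputed sentence is the Riskometer validation paper, and section 4 shows that event outcomes had been ruled out. This largely stands: the score is the likelier intention. It does not rescue the sentence, because the one number offered is then not a power input at all.

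A reader might go further than the documents allow in three ways.

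- **That the 90% is false.** This is not shown. On the score reading it is attainable with a modest CV, or with a larger one and a well-correlated baseline. The 40% and 62% figures above rest on assumed CVs and no adjustment, and do not estimate the trial's actual power.
- **That 0.07% is impossible.** One case in 1,265 is 0.079%, so it may be a truncation. It needs checking.
- **That a main result is at risk.** The score is absent from the section 31 end points and is only one example input to the economic model, whose uncertainty is to be simulated. The primary analysis and the sample size do not depend on this sentence.

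It could also be said that such detail belongs in a statistical analysis plan. That would answer a missing detail. Here the protocol asserts a specific power on a stated input that cannot give it.

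**Conclusion.** The point holds as a charge that the stated power is unsupported. As an event comparison, 90% is out of reach: about 5% at the quoted incidence (2.8% in the intended direction) and 21% at the document's highest multi-year rate, assuming 180 per arm, two-sided 5% and no loss. As a comparison of Riskometer scores, the more probable meaning, 90% can be neither confirmed nor refuted. It requires SD/mean of at most about 0.52 with 144 evaluable per arm unadjusted, or about 0.65 to 0.87 if the baseline correlation is 0.6 to 0.8. Those correlations are assumptions. The consequence is limited to how this secondary outcome is read.

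**What to change.** Either delete the sentence, or rewrite it: name the outcome as the Stroke Riskometer predicted 5-year risk at 6 months; give its expected mean and SD in patients after TIA or minor stroke, the assumed baseline correlation and the test; and restate the power for about 288 evaluable participants. In both cases correct or remove the 0.07%, and add that the trial is not powered for stroke events, in line with section 4.

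The cost is wording only. A stated secondary power is withdrawn or may be lowered; sample size, data collection and trial conduct are unaffected.

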### 33. DESCRIPTIVE ANALYSES

These will be reported overall and compared between HWC and usual care groups using parametric and non-parametric techniques, depending on the distribution of the data. Means (95% CI), standard deviations, medians and quartiles will be reported for continuous risk factor variables while cross-tabulations will be reported for categorical risk factor variables.

---

### 34. INFERENCE ANALYSES

Intention to treat (ITT)[95] analyses and per protocol analysis will be used. To address the primary hypothesis ANCOVA will be used to compare the difference in systolic blood pressure at 6-months post randomisation between the HWC and usual care groups, accounting for baseline stratification factors: (age, gender and ethnicity), referral centres, geographical region and known influential clinical characteristics (e.g., comorbidities). To address the secondary hypotheses linear mixed effects (LME) repeated measures models will be used to investigate the differences in (1) adherence to medication (2) health-related quality of life (3) incidence of new vascular events including death (4) life satisfaction (5) cognition (6) mood) and (7) health service utilisation costs between the HWC and Usual care groups, and by ethnicity (sub-group analysis) at 6-months (plus

life-style and adherence at 1-year post-randomisation. These LMEs will model effect of time (baseline, 3-, 6- 9- and 12-months (medication adherence, lifestyle and awareness at only 12 months), post-randomisation whilst accounting for key demographic stratification factors known to confound with outcomes. Any data not collected within 6-weeks of the follow-up points will be classified as missing data. Baseline covariates of age, sex, most recent blood pressure measure and any additional variables predictive of outcome data will be included in the imputation model.[46] The reasons for missingness and the reasons will be recorded and accounted for. Sensitivity analyses will be conducted to test the assumptions of the model (including a complete case analysis in which only subjects with complete data are included). Familywise error control will be used to account for the multiplicity of tests. Inferences will be based on a 5% significance level and two-sided alternatives.

For the analysis of - CVD adverse outcomes (fatal and nonfatal stroke, TIA, myocardial infarction and heart failure, death attributable to CVD and all-cause mortality), we will use Kaplan-Meier life-test and estimate the hazard ratios (HR) and adjusted HR using time-to-event Cox regression analysis. Time to event analysis will include recurrent events and time-dependant variables where appropriate.

Competing risk method will also be applied to compare the CVD adverse outcomes between the two interventional groups, accounting for mortality outcome.

---

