### 7. SAMPLE SIZE CALCULATION AND POWER ANALYSIS:

[figure not shown]
360 participants are required to provide 85% power (two sided  $\alpha=0.05$ ) to detect at least a 6 mm Hg clinically significant difference in systolic BP (SBP) changes at 6 months from baseline, between the HWC and UC groups. This estimation assumes a 20% non-compliance/loss to follow-up. Based on our previous HWC trial (Prevents RCT on HWC for primary stroke prevention, publication in preparation) [57] data in NZ stroke patients ( $n=251$ , 9-month BP change in HWC patients is 4.4 mm Hg (SD:18) and in usual care patients is 10.6 mm HG (SD 22).

The sample size estimations used the proc power procedure of SAS – a statistical analysis software. Using the means of the SBP changes in the two groups and the pooled standard deviation (SD 20) from the previous HWC trial, the calculation indicates  $n=352$ . R software was also used for simulating changes in BP for the two groups and yielded a simulated type II error  $< 0.10$  (statistical power  $> 0.90$ ) when  $n=300$  (simulation of 1000 and 10000 times). We adopted the simulated results because it uses two different group standard deviations, and it is under the budget limit control. After adjusted 20% attrition rate, the proposed sample size is  $n=360$ . The power calculation is also informed by literature that a 5mmHg reduction in SPB is clinically meaningful and leads to a 11% reduction in the incidence of stroke.

The results of the trial will be reported according to the Consolidated Standards of Reporting Trials (CONSORT) statement as outlined in the below flowchart. If required, we will apply The CONSERVE 2021 Statement; Guidelines for Reporting Trial Protocols and Completed Trials Modified, in the case of the study being affected COVID-19 Pandemic and Other Extenuating Circumstances.

---

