## 9. AIMS AND HYPOTHESES

### 10. PRIMARY AIM

The **primary aim** is to determine the effectiveness of HWC in improving blood pressure at 6 months post-randomisation.

The primary hypothesis is that HWC initiated one-month post ( $\pm$  two weeks) of the onset of first-ever in a lifetime minor stroke or onset of TIA will lead to clinically meaningful improvements in lifestyle behaviours resulting in a mean difference of 6 mm Hg change in blood pressure from Baseline to 6 months post-randomisation in the HWC compared to usual care. Recurrent TIA onset is included.

The primary end-point is the difference in the mean change from Baseline in systolic blood pressure at 6 months post-randomisation between UC and HWC. The study is powered to detect a mean difference in change of 6 mm Hg ( $SD \pm 20$  mm Hg) between HWC and UC groups at 6 months post-randomisation.

---

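### The primary ANCOVA does not name baseline systolic BP as a covariate, and the protocol does not settle whether 6-month SBP or its change is analysed

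*Protocol*

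**What the plan says.** Section 34 (Statistical Analyses) states the primary model: "ANCOVA will be used to compare the difference in systolic blood pressure at 6-months post randomisation between the HWC and usual care groups". The adjustment set begins "accounting for baseline stratification factors: (age, gender and ethnicity), referral centres, geographical region" and ends with an open category of influential clinical characteristics, illustrated only by comorbidities. Baseline SBP is not named. Further on, the same section does name a blood pressure reading, but for the imputation model.

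Section 10 defines the endpoint differently: "The primary end-point is the difference in the mean change from Baseline in systolic blood pressure at 6 months post-randomisation between UC and HWC". Section 30 also defines it as mean change. Section 7 powers the trial on a "6 mm Hg clinically significant difference in systolic BP (SBP) changes at 6 months from baseline", using "the pooled standard deviation (SD 20) from the previous HWC trial".

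Section 29 places the baseline assessment before randomisation. Appendix A calls for three seated readings, and Forms B and F (Appendix C, section 15, Part A) record their average. The Randomisation section balances on age, sex and ethnicity, not on blood pressure.

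**The concern.** Baseline SBP is normally the strongest single predictor of later SBP. Leaving it unnamed matters in two ways.

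First, the dependent variable is not fixed. With baseline SBP in the model, analysing change or the 6-month value gives the same group coefficient, and the mismatch between sections 10 and 34 is harmless. Without it, the two estimates differ by exactly the observed baseline difference between the arms. Two analysts following the protocol could then report different primary results.

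Second, precision is lost. For any correlation between 0 and 1 and equal variances at the two visits, the baseline-adjusted analysis has variance no larger than either alternative. That matters in a trial whose power, recomputed from its own inputs, is below what it states.

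**Working it through.** **Inputs from the protocol.** Two-sided 5% ("Inferences will be based on a 5% significance level and two-sided alternatives"); difference 6 mm Hg; SD of change 20; 360 randomised 1:1; 20% non-compliance or loss (section 7). Treating all 20% as loss leaves 360 × 0.8 = 288, or 144 per arm.

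**Assumed, because the protocol does not give them.** Correlation r between baseline and 6-month SBP; equal variances at the two visits; no precision gain from the other covariates.

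**The protocol's own figures.** Section 7's n = 352 reproduces exactly as a t-test at 80% power (6 mm Hg, SD 20) before any attrition. The stated powers ("360 participants are required to provide 85% power" in section 7 and "The sample of 360 participants will provide a simulated 90% statistical power" in section 32) do not reproduce. By the normal approximation with 144 per arm:

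- standard error = 20 × √(2/144) = 2.357
- 6 / 2.357 = 2.546; 2.546 − 1.960 = 0.586; power = 72.1%

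The t-based figure is 71.8%. With no loss at all (180 per arm) power is 81.2%.

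**The three candidate analyses.** Let s be the SD of SBP at each visit.

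- Change score: variance 2s²(1 − r) = 400, so s² = 200/(1 − r).
- 6-month SBP without baseline: SD s = 20/√(2(1 − r)).
- ANCOVA with baseline SBP: residual variance s²(1 − r²) = 200(1 + r), so SD = 20 × √((1 + r)/2).

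Example at r = 0.5: ANCOVA SD = 20 × √0.75 = 17.32; standard error = 17.32 × √(2/144) = 2.041; 6/2.041 − 1.960 = 0.979; power = 83.6%.

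| r (assumed) | ANCOVA SD | SD of 6-month SBP | Power, change score | Power, 6-month SBP unadjusted | Power, ANCOVA with baseline | Gain over change score (points) | Gain over 6-month SBP (points) |
|---|---|---|---|---|---|---|---|
| 0.3 | 16.12 | 16.90 | 72.1% | 85.4% | 88.4% | 16.3 | 3.0 |
| 0.5 | 17.32 | 20.00 | 72.1% | 72.1% | 83.6% | 11.5 | 11.5 |
| 0.6 | 17.89 | 22.36 | 72.1% | 62.4% | 81.2% | 9.1 | 18.8 |
| 0.7 | 18.44 | 25.82 | 72.1% | 50.5% | 78.8% | 6.7 | 28.3 |
| 0.8 | 18.97 | 31.62 | 72.1% | 36.3% | 76.5% | 4.4 | 40.2 |

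**Share of the shortfall recovered, against the change score.** Towards 85%: more than all at r = 0.3, then 89%, 71%, 52% and 34% at r = 0.5, 0.6, 0.7 and 0.8. Towards 90%: 91%, 64%, 51%, 38% and 25% at r = 0.3, 0.5, 0.6, 0.7 and 0.8.

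**Why the outcome scale stops mattering.** If change = a + b·group + c·baseline, adding baseline to both sides gives 6-month SBP = a + b·group + (c + 1)·baseline. The group coefficient b is unchanged.

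**Chance imbalance.** With equal variances the slope on baseline is r. For each 1 mm Hg by which the arms differ at baseline, the unadjusted 6-month difference moves by r mm Hg and the change-score difference by r − 1 mm Hg. At r = 0.6 that is +0.6 and −0.4. ANCOVA with baseline removes both.

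**The case against.** The strongest reply is that nothing has been left out. The covariate list is open-ended, baseline SBP fits the category of influential clinical characteristics, an ANCOVA for a change-from-baseline endpoint is ordinarily understood to adjust for baseline, and a statistical analysis plan not shown here may name it. This stands in part: the protocol does not exclude baseline SBP, so the fair statement is that it is not named. The reply does not remove the mismatch between change in sections 10 and 30 and the 6-month value in section 34. Nor is it satisfactory for the main expected covariate of the primary model to rest on an open phrase illustrated only by comorbidities.

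The size of the gain is also open to challenge. The 72% comes from a test with no covariates, whereas the planned model already adjusts for several, and the comorbidity list includes hypertension. Some of the variance credited to baseline SBP may already be absorbed. Form B also stops anyone whose average baseline SBP is below 130, which would narrow the baseline variance and strain the equal-variance assumption. Both points stand, so the table shows an order of size and not a forecast.

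Three stronger readings are tempting and not supported:

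- *Baseline adjustment would restore most of the missing power.* This depends on a correlation the protocol does not give. Against 85% it holds up to about r = 0.7, against 90% only up to about r = 0.6. If 6-month SBP would otherwise be analysed and r is 0.3, the gain is only 3 points.
- *Regression to the mean biases the comparison.* It acts on both randomised arms alike. The change-score and 6-month analyses have the same expected treatment effect.
- *Centre and comorbidities should leave the primary model.* No error is shown in keeping them; this is the sponsor's choice.

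**Conclusion.** The point holds as a free improvement that should be made. The protocol does not name baseline SBP in its primary model and describes the dependent variable in two ways. The planned analysis is valid on either reading, but it is not uniquely defined and is likely to be less precise than it could be.

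Under the stated assumptions the gain is about 7 to 16 points over an unadjusted change score for r from 0.7 down to 0.3 (about 4 at r = 0.8). Over an unadjusted 6-month comparison it is about 3 to 28 points as r goes from 0.3 to 0.7. At 144 per arm, 90% is not reached at any r from 0.3 upward, and 85% is missed from r = 0.5 upward.

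The stated power in sections 7 and 32 therefore remains a separate matter. The figures above also treat the whole 20% as loss. If it were non-compliance with no benefit, the effect would shrink to 0.8 × 6 = 4.8 mm Hg, and an unadjusted change score on all 360 would have about 62% power.

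**What to change.** Replace the primary-analysis sentence in section 34, before any unblinded data are seen, with: the primary analysis is an ANCOVA of SBP at 6 months (mean of the three readings) on randomised group, baseline SBP (mean of the three readings, continuous), age, sex and ethnicity. Add that the group coefficient estimates the between-arm difference in mean change, so that it answers the endpoint in sections 10 and 30. If centre, region or comorbidities stay in the model, list them explicitly.

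The cost is one sentence, since both SBP values are already collected in everyone assessed. If the sample-size section is to take credit for the adjustment, it should state the correlation assumed and its source. Sections 7 and 32 need correcting in any case.
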